Study Procedures:

For residents of LTCF all procedures will be conducted on-site at the LTCF and for the community cohort, all procedures will be conducted in the research clinic. No study procedures will be performed prior to consent.

It is anticipated that most LTCF residents will have a screening/enrollment visit and that vaccination will occur separately as per the LTCF vaccination plans. In most cases, the community cohort will have screening and vaccination on the same visit.

Schedules of Activities are listed below.

Schedule of Activities

| Category of Activity | Research | Standard of Care | Research |
|--|-----------------------------------|------------------|------------------------------------|
| Visit Number | V0 ^a | V1 ^a | V2 |
| Visit Type | Screening and Enrollment | Vaccination | 1-month (D28) |
| Visit Window | up to -21 days before vaccination | | D21-42 after vaccination/infection |
| Visit Location | LTCF/clinic | LTCF/clinic | LTCF/clinic |
| Informed Consent | up to -21 days before vaccination | | |
| I/E | X | | |
| Medical History | X | | X |
| Vaccine History | X | | X |
| Prohibited Medication Review | X | | X |
| Vital Signs | X | X ^c | |
| Targeted PE ^b | X | X ^c | |
| Collect 10cc serum | X | | X |
| Vaccinate | | X | |
| 15-minute Observation (post vaccination) | | X ^c | |
| Review ARI history and test results | | | X |
| SAE review | | | X |

^a Informed consent and screening activities can be separate or combined with Visit 1.

^b Targeted physical exam will be performed on screening and before vaccination only as clinically indicated based on the presence of signs or symptoms warranting further investigation.

^c Vaccination related procedures will be guided by SOC at each location

CONSENT PROCESS

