- Obtain and record the participant's demography (including complete date of birth, sex, race, racial designation, and ethnicity)
- Obtain and record medical history
- Obtain and record details of any non-study vaccinations, and prohibited concomitant medications and treatments
- Perform a clinical assessment including vital signs (Blood pressure, heart rate and oxygen saturation) and symptom-targeted physical exam
**Note: Height and weight will be recorded as by participant report or medical record in LTCF.*
- Collect 10 cc of serum
- Confirm contact and alternate contact information with participant and LTCF staff
- Schedule visit 2.

Visit 1 (Standard of Care) [Vaccination: For LTCF this will be performed by LTCF staff per their facility protocol and for Community Cohort this will be performed in the clinic]

- Perform a clinical assessment including vital signs (Blood pressure, heart rate and temperature) and symptom-targeted physical exam as dictated by location of vaccination standard procedures.
- Vaccinate with ABRYSVO or AREXVY and in non-dominant arm and document product, time and location.
- 15 minutes of observation in the clinic, in LTCF standard practice will be followed

If a person has an intercurrent RSV infection and is not vaccinated as part of SOC, visit 2 will be scheduled 28-42 days after infection was documented.

Visit 2 (Research Procedures) [1-month]

- Verbally confirm the participant wishes to continue in the study
- Obtain and record any new medical history
- Inquire about any respiratory illnesses and record results any viral testing performed.
- Collect information on AEs, SAEs related to study procedures
- Obtain and record details of any non-study vaccinations, and prohibited concomitant medications and treatments
- Perform a symptom-targeted clinical assessment and physical exam
- Collect 10 cc of serum.

Individuals who do not meet the criteria for participation in the study (screen failure) can be rescreened if the exclusionary condition is considered to be temporary in nature by the investigator.

Only the following information will be collected on screen failures: demographics (age, screen number, sex, ethnicity, and race) and reason for ineligibility. Participants who are found to be ineligible will be told the reason for ineligibility.

LABORATORY METHODS:

RSV PCR will be performed as standard of care in the LTCF.

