Enzyme Immunoassay (EIA): Serum IgG titers to RSV F (prefusion) protein of group A and B RSV will be determined by enzyme immunoassay using established methods.²⁸ Briefly, purified RSV proteins are coated to 96-well EIA plates to which serum 2-fold dilutions are added in duplicate. Bound antibody is detected with alkaline phosphatase-conjugated goat anti-human IgG antibody and substrate.

Microneutralization Assay (MNA): Serum neutralizing titers will be performed using an established microneutralization method for RSV A and B strains.²⁸ Briefly, 2-fold serum dilutions are incubated with 75 plaque forming units of RSV for 30 min at room temperature followed by the addition of 10⁴ HEp-2cells in 96-well culture plates. After 3 days, the quantity of RSV antigen is determined by enzyme immunoassay using a monoclonal antibody to the RSV F protein. The neutralization titer is defined as the serum dilution that results in a 50% reduction in color development.

ANALYTICAL AND STATISTICAL METHODS

The primary immunogenicity analysis will include persons vaccinated but without documented RSV infection (PCR or G ELISA). The immune response to infection alone or combined infection and vaccination will be analyzed descriptively and separate from the primary analysis. This study is designed to demonstrate non-inferiority to within a 1.5-fold difference in the 1-month titer level, adjusting for baseline titer level. Since the distribution of titer levels is strongly positively skewed, and we are interested in relative changes, all titer levels

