Based on data from 52 participants in a prior study of the Pfizer RSV vaccine, the geometric mean titer level was estimated to be 2218 (95% CI: 1822-2699) at baseline, and 22,510 (17,003-29,799) at 1-month, corresponding with a relative change of 10.15-fold (95% CI: 7.39-13.95). From this data we estimate the Standard Deviation (SD) of log(titer) to be 0.71 at baseline and 1.01 at 1-month, while the SD of the 1-month change in log(titer) is 1.14 –larger than SD (log (1-month titer)), indicating that a 2-sample t-test of the change in log(titer) would be less efficient than a t-test of the 1-month log(titer). Since we plan to adjust for baseline log(titer), our residual SD $< \min(\text{SD}(\log(1\text{-month titer})), \text{SD}(\log(\text{relative change in titer}))) = \min(1.01, 1.14) = 1.01$. But not much less, since the prior data suggests the correlation between baseline and 1-month log(titer) is very weak ($r=0.14$), with log (baseline titer) explaining only 2% of the variability in log (1-month titer). In particular, we estimate residual SD = 1, suggesting that a 2-sample t-test of log (1-month titer) would be nearly as efficient as our linear model-based test adjusting for log (baseline titer). Given this estimate of variability (SD=1), a sample size of 76, 89, or 105 per group provides 80%, 85%, or 90% power to demonstrate non-inferiority to within a relative non-inferiority margin of 1.5-fold using a 1-sided 0.05 level linear model-based t-test comparing log (1-month titer) by population, adjusted for log (baseline titer). We have chosen a sample size of 76 in each group which will provide 80% power to demonstrate non-inferiority.

POTENTIAL RISKS AND BENEFITS

This study may be associated with risk due to sample collection or loss of privacy.

Sample Collection:

- **Blood draws:** A blood draw may cause faintness, inflammation of the vein, pain, bruising, or bleeding at the site of the puncture. There is also a slight chance of infection.

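### Does the Visit 2 window after RSV infection, which starts at day 21 in the schedule and day 28 in the visit text, undermine the analysis?

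*Combined protocol and SAP*

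**What the plan says.** Two places in the protocol time Visit 2 for someone who has RSV during the study.

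- **Schedule of Activities, Visit Window row:** "D21-42 after vaccination/infection". One window serves both starting events, under a column whose nominal day is 28.
- **Study Procedures, end of the Visit 1 text:** "If a person has an intercurrent RSV infection and is not vaccinated as part of SOC", then "visit 2 will be scheduled 28-42 days after infection was documented".

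Analytical and Statistical Methods then says how such data are used: "The immune response to infection alone or combined infection and vaccination will be analyzed descriptively and separate from the primary analysis". The primary analysis is limited to vaccinated participants with no RSV infection documented by PCR or by antibody to the G protein.

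**The concern.** Both passages are current text, and both cover the infected, unvaccinated participant: someone with no vaccination date can be timed only from infection. The protocol does not say which passage takes precedence. The starting point also differs, since the schedule counts from infection and the visit text from the date on which infection was documented.

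If the infection-only titers mattered to a conclusion, this could matter too. Antibody levels change in the weeks after infection, so samples drawn from day 21 and samples drawn from day 28 are not strictly alike. It would be unclear which visits were protocol deviations. The infection-only group would share the vaccine group's window under one passage and not under the other.

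**Working it through.** **1. The two windows side by side.**

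| Source | Days | Length |
|---|---|---|
| Schedule of Activities | 21 to 42 | 42 − 21 + 1 = 22 days |
| Visit 1 text | 28 to 42 | 42 − 28 + 1 = 15 days |
| In both | 28 to 42 | 15 days |
| Schedule only | 21 to 27 | 22 − 15 = 7 days |

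The second window is a subset of the first. Counted from the same date, every visit booked under the Visit 1 text is in window under the schedule. A conflict arises only if a visit is in fact made on days 21 to 27.

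**2. Does either window enter the plan's own calculation?** The inputs in Power and Sample Size Considerations are "a relative non-inferiority margin of 1.5-fold" (ln 1.5 = 0.4055), "we estimate residual SD = 1", and 80% power "using a 1-sided 0.05 level linear model-based t-test". With no true difference:

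n per group = 2 × (1.645 + 0.842)² × 1² / 0.4055² = 75.2, rounded up to 76.

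This matches the stated 76. The noncentral t distribution on 2 × 76 − 3 = 149 degrees of freedom gives 80.0% power. No term depends on the timing of a post-infection visit, and the participants concerned are outside the primary analysis set in any case.

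**3. How many people could be affected?** The protocol gives no count, so this is an illustration with stated assumptions. Background and Rationale cites LTCF infection rates of 1-12%. Assume that these apply to one study season, spread evenly over November to April (182 days), and that every resident waits the maximum 21 days between screening and vaccination. Assume also that everyone infected in that gap goes unvaccinated.

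- Low: 76 × 0.01 × 21/182 = 0.09 residents.
- High: 76 × 0.12 × 21/182 = 1.05 residents.
- High, with all infections packed into half the period: 76 × 0.12 × 21/91 = 2.10 residents.

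Only visits on days 21 to 27 are in dispute. If visits fell evenly over the 22 days, that share would be 7/22 = 0.32, or 0.32 × 1.05 = 0.33 residents in the high case. The community cohort adds little, because most of its members are screened and vaccinated at one visit.

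**4. Does any rule act on the window?** None is written. The methods section does not exclude a Visit 2 sample for being early or late, so a day-24 sample would still be reported. The objectives compare LTCF residents with community adults after vaccination; none compares infection with vaccination. Visit 2 includes a review of respiratory illness and test results, so the actual interval from documented infection can be calculated and shown beside each titer.

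**The case for a change.** The strongest case for acting is that the contradiction is plain and the correction would cost one line. Reading days 28-42 as a booking target inside a wider allowed window is sensible, but no passage says so, and the schedule already gives day 28 as its nominal day. The protocol clearly foresees these cases: it runs through the RSV season and allows up to 21 days between screening and vaccination. In a group of one or two people, a single early sample can visibly move a geometric mean.

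Much of this stands. The lower limits differ, precedence is not stated, and the starting date is worded differently in the two places, so matching the day numbers alone would not remove the whole discrepancy. What does not follow is harm to a result. A geometric mean from one or two people supports no inference whichever window is used. The plan draws none from it, and no sample is gained or lost by rule.

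**Conclusion.** The mismatch is a clerical slip: 7 days' difference at the lower limit, plus a loosely worded starting point. It affects only the timing of a descriptively reported infection-only group, which on the assumptions above numbers from near zero to about two people. The primary analysis set, the adjusted titer ratio, the 76 per group and the 80% power are the same under either window.

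This conclusion rests on two features of the plan: documented infections stay out of the primary analysis, and no rule makes inclusion of a sample depend on the window. The head count is softer, because the period to which the 1-12% refers is not stated, but the conclusion would hold with a larger group.

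The two passages should be made to agree, on the starting date as well as the days, as routine wording upkeep. The documents do not show which window was intended, and none is preferred here. Followed as written, the plan gives the same results and the same conclusion, so no change to the design or analysis follows.

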Objectives: The primary objective of this study is to compare the neutralizing antibody response at one-month post-vaccination with a licensed RSV vaccine in adults \geq 60 years of age living in skilled nursing facilities with adults living in the community. A secondary objective will be to evaluate the binding antibody responses to RSV preF proteins at 1 month.

Study Design

The study will be conducted at URMC and 2 local LTCFs. Approximately 76 persons \geq 60 years of age who live in LTCF and an equal number of older adults living independently in the community who are planning to receive one of the licensed RSV vaccines as part of standard of care (SOC) will be recruited for participation in the study.

Study procedures: Visits will occur at the LTCF for residents of LTCF or in the research clinic for community-dwelling older adults. After informed consent by the participant or legally authorized representative (LAR), demographic and medical history will be collected and a symptom-targeted physical exam will be performed. A 10 cc blood sample will be collected prior to vaccination. Following vaccine administration, individuals will be monitored for 15 minutes for immediate adverse events. One additional visit will occur at 1 month post vaccination at which time 10 cc of blood will be collected, the participant will be interviewed and medical records reviewed. Subjects will be queried about any intervening respiratory illnesses and persons testing positive for RSV infection as part of the standard of care (SOC) after vaccination or by a non-vaccine RSV protein by ELISA and before the 1-month blood draw will not be included in the immunogenicity analysis. Serum samples will be tested for binding (RSV A and RSV B PreFusion F, Attachment (G) protein) and neutralizing antibodies to RSV A and RSV B in the URMC research laboratory.

BACKGROUND and RATIONALE

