This is an open label non-inferiority study where all participants will receive either the licensed Pfizer RSV Vaccine (ABRYSVO) or the GSK RSV Vaccine (AREXVY) as part of Standard of Care (SOC) and immune responses will be compared between adults living in the community and adults living in LTCF. The vaccines available at the participating LTCF as part of SOC will direct what product is administered at the individual LTCF and the community cohort will be matched for similar proportions of ABRYSVO and AREXVY.

Primary Objectives:

Demonstrate that the peak immune response at 1 month post vaccination of adults 60 years and older residing in LTCF is non-inferior to community-dwelling adults 60 years and older as measured by:

- Serum neutralizing antibody against RSV A & B

Secondary Objectives:

Demonstrate that the peak immune response at 1-month post vaccination of adults 60 years and older residing in LTCF is non-inferior to community-dwelling adults 60 years and older as measured by:

- Serum binding antibody to RSV prefusion F protein against RSV A & B

Study Period and Sites:

The study will be conducted at the University of Rochester Medical Center (URMC) in collaboration with 2 local LTCFs and include the Highlands at Brighton and St. Ann's Home. These LTCFs are located geographically close to URMC and have expressed a high interest in participating in this study. The study period will be from November 2023 to April 2024. There will be 1 month of direct participant involvement and 6 months for completion of the immune assays and data analysis.

Participant Recruitment:

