For the cohort of LTCF residents, participant recruitment will be coordinated with the staff of the participating LTCF. At Highlands of Brighton the LTCF will identify individuals who express interest in the study. The LTCF staff contact individuals and legally authorized representatives to obtain consent for influenza, RSV, and COVID vaccination during the annual vaccination campaigns. During the conversation regarding SOC RSV vaccination with an FDA-approved RSV vaccine, LTCF staff will also assess potential interest in participating in the clinical study related to RSV vaccination for residents accepting the RSV vaccine as part of SOC. Those individuals who express interest in both receiving a licensed RSV vaccine as SOC and also participating in a research study will be directed to a member of the study team who will provide more detailed information about the study and if appropriate provide an IRB-approved consent form for review and consideration. St Ann's Home uses an opt-out approach when communicating with residents and LAR about vaccines. If residents or LAR's do not opt-out they will be scheduled for RSV vaccination. St Ann's will include in the opt-out letter a statement that a member of the research team will contact them about the study if they do not opt-out of RSV vaccination. Included in the communication will be the ability to-opt out of contact with the research team.

The major source for recruitment for the community cohort at URMC will be our RedCap Database Registry (STUDY00000413) of participants who have previously agreed to be contacted for future research

opportunities. We will send them an email to ascertain interest in the proposed study if RSV vaccination is planned as part of routine medical care. Potential participants will be provided the clinic phone number and the web-based registry to express interest (<https://www.urmc.rochester.edu/idrc-research-studies.aspx>). We will include all genders, races, and ethnicities in the study. We will use our IRB-approved screening protocol (STUDY00000484) to perform an initial pre-screening for basic inclusion and exclusion criteria after which, for those interested and meeting study criteria, we will set up a screening/enrollment appointment in the clinic. We will e-mail information on their scheduled appointment and a copy of the IRB-approved consent for the participant to review. Questions about the study will be answered prior to or during the enrollment visit.

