Inclusion and Exclusion:

Inclusion criteria are intended to be broad with relatively few exclusions to reflect a real-life population in LTCF.

Inclusion:

- ≥ 60 years of age who live in skilled nursing facilities or reside independently in the community
- Life expectancy of >6 months, as assessed by the investigator
- Able to sign informed consent or to provide consent via a legally authorized representative (LAR)
- Planning to receive an RSV vaccine as part of standard medical care

Exclusion criteria:

- History of a current immunosuppressive condition or receipt of chemotherapy or other immunosuppressive or cytotoxic therapy, including chronic prednisone use of ≥ 20 mg/day for more than 14 days within 3 months of study vaccination
- History of hypersensitivity or reaction to any vaccine component
- Simultaneous administration of another vaccine (influenza, SARS-CoV-2) or within a 14-day window before or after intervention
- Previous receipt or intended receipt of an RSV vaccine outside the study
- Receipt of blood/plasma products or immunoglobulin within 60 days before study intervention administration.
- Documented RSV infection within 2 months prior to study intervention (enrollment).

Criteria for Temporarily Delaying Enrollment/Administration of Study Intervention:

The following conditions may allow a participant to be enrolled once the conditions have been resolved and the participant is otherwise eligible. Participants meeting these criteria at Visit 1 will be considered screen failures if enrollment has closed once the condition(s) has/have resolved.

- Current febrile illness (temperature $\geq 38.0^{\circ}\text{C}$ [$\geq 100.4^{\circ}\text{F}$]) or other acute illness within 48 hours before study intervention administration
- Receipt of any vaccine (including COVID-19 vaccines authorized for temporary or emergency use) within 14 days before study intervention administration
- Anticipated receipt of any non-study vaccine within 14 days after study intervention administration
- Receipt of short-term (<14 days) systemic corticosteroids (the equivalent of ≥ 20 mg/day of prednisone)
- Study intervention administration should be delayed until systemic corticosteroid use has been discontinued for at least 28 days.

Note: Systemic corticosteroids administered at a dose of <20 mg/day of prednisone or equivalent are permitted. Inhaled/nebulized, intra-articular, intrabursal, or topical (skin or eyes) corticosteroids are permitted.

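### Does the plan leave open whether participants who receive another vaccine after RSV vaccination, or are drawn outside the visit window, belong to the primary analysis?

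*Combined protocol and SAP*

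**What the plan says.** The Analytical and Statistical Methods section defines the primary set by two conditions, vaccination and no documented infection: "The primary immunogenicity analysis will include persons vaccinated but without documented RSV infection (PCR or G ELISA". The Study procedures paragraph in the synopsis agrees. It removes people found to have RSV infection after vaccination and "before the 1-month blood draw will not be included in the immunogenicity analysis". No other removal after vaccination is tied to the analysis.

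Two other places bear on who might be questioned later:

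- The exclusion criteria list "Simultaneous administration of another vaccine (influenza, SARS-CoV-2) or within a 14-day window before or after intervention". The temporary-delay criteria that follow cover the same period prospectively: "Anticipated receipt of any non-study vaccine within 14 days after study intervention administration".
- The Schedule of Activities gives the Visit 2 window as "D21-42 after vaccination/infection".

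Eligibility is checked at Visit 0. Visit 2 records non-study vaccines actually received, and no consequence for the analysis is attached to that record. The eligibility section opens with its intent: "Inclusion criteria are intended to be broad with relatively few exclusions to reflect a real-life population in LTCF".

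**The concern.** Half of the vaccine criterion looks forward. Nobody can know at Visit 0 whether a resident will receive an influenza or COVID-19 vaccine in the two weeks after the RSV dose. A person can therefore enter correctly and later match an exclusion criterion as worded. This is easy to picture in the LTCF cohort, where staff "obtain consent for influenza, RSV, and COVID vaccination during the annual vaccination campaigns", and where the facility rather than the study team gives the vaccine.

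An analyst could then point to the exclusion criteria to drop that person or to the primary-set sentence to keep them. A draw outside days 21 to 42 appears to raise the same question. "This is an open label non-inferiority study", so group membership is known. Coding the samples protects the assay but not the choice of set. If the choice were made after the titers were seen, it would be a second chance at the same non-inferiority test, whether or not the breach had any effect on titers.

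**Working it through.** **Inputs from the plan.** Residual SD of log titer 1; 76 per group; one-sided level 0.05; non-inferiority if the lower bound for the ratio exceeds 2/3, so the margin is ln(1.5) = 0.405.

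**The plan's own figure.** SE = √(1/76 + 1/76) = 0.1622 and 0.405/0.1622 = 2.50. With a noncentral t on 76 + 76 − 3 = 149 degrees of freedom and a true ratio of 1, power is 80.0%. At 89 and 105 per group it is 85.3% and 90.0%. The stated 80%, 85% and 90% are reproduced.

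**Assumptions.** The documents give no number of affected participants, so it is varied. Breaches are taken to have no effect on titers. One endpoint is considered.

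**Error if the better of two sets is always taken.** Let the full set be 76 v 76 and the reduced set n₁ v n₂. For nested sets the two test statistics have correlation r = SE(full)/SE(reduced). At a true ratio of 2/3 each alone passes with probability 5%. The chance that at least one passes is 1 − Φ₂(1.645, 1.645; r), where Φ₂ is the bivariate normal distribution function.

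| Removed | Reduced set (LTCF v community) | SE(reduced) | r | At least one passes |
|---|---|---|---|---|
| 1 resident | 75 v 76 | 0.1628 | 0.997 | 5.3% |
| 2 residents | 74 v 76 | 0.1633 | 0.993 | 5.5% |
| 8 residents | 68 v 76 | 0.1669 | 0.972 | 6.0% |
| 15 residents | 61 v 76 | 0.1719 | 0.944 | 6.4% |
| 4 per group | 72 v 72 | 0.1667 | 0.973 | 5.95% |
| 8 per group | 68 v 68 | 0.1715 | 0.946 | 6.3% |
| 15 per group | 61 v 61 | 0.1811 | 0.896 | 6.85% |

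Simulation of the planned model with the baseline term gives 6.0%, 6.2% and 6.8% for 4, 8 and 15 per group, and 6.0% and 6.35% for 8 and 15 residents. The full set alone stays at 4.8% to 5.1%.

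**How often the two sets disagree.** At a true ratio of 1 with 15 removed per group, the same normal approximation gives 10.5 points where the full set passes and the smaller one fails, plus 2.5 where the smaller set passes and the full one fails: 13.0 points in all. With 8 per group the split is 6.1 and 2.2. The larger part is mainly lost power: at a true ratio of 1, power is 80.0% at 76 v 76, 76.0% at 68 v 68 and 72.0% at 61 v 61. If the written rule is the default, only the smaller part is a second chance to pass.

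**The two supposed conflicts, read against the text.**

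1. *Later vaccine.* The criterion is an enrollment criterion, checked at Visit 0, and the delay criterion shows how its forward-looking half is applied: by asking what is anticipated. Where the authors want a removal after vaccination, for infection, they write it. They write none here.
2. *Draw outside days 21 to 42.* The window is an entry in a visit schedule. No sentence takes an out-of-window sample out of the analysis, and the primary-set rule keeps it. There are not two readings to choose between, so a calculation with two separately decided deviations and four possible sets has no basis in the documents.

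**The case for a change.** The best case for a change is that the primary-set sentence deals with infection alone. It does not say that an exclusion met after enrollment is to be ignored, no evaluable or per-protocol set is defined, and no point is named at which the set is fixed. The later-vaccine situation is foreseeable, one sentence would settle it, and the sole primary conclusion is at stake.

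The silence is real for later vaccines, and a clarifying clause would do no harm if well drafted. Three things limit its value. Such a clause would mainly repeat the existing rule. Those who want it would accept either keeping or removing these people, so the present rule is not itself at fault. And the obvious wording, that nobody leaves the set once titers are available, would cut across the plan: documented infection includes G ELISA, run on the same sera in the same laboratory as the titers, so a required removal for infection could come to light at the same time or later.

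**Conclusion.** No change follows. This is a gap in detail that an analyst fills sensibly by applying the primary-set rule as written: vaccinated, no documented RSV infection, with the two titers the model needs. That rule gives a 5% one-sided test, keeps the planned 80% power if breaches do not affect titers, and suits the stated wish for a broad, real-life LTCF population.

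The inflation, about 5.3% to 6.4% for 1 to 15 affected residents and up to 6.85% if 15 in each group were affected, rests on an assumed number of breaches and on a favorable choice always made after seeing the results, against the plain text. If nobody is affected, or the written rule is followed, the inflation is nil. The documents show neither that breaches occur nor that they would bias the ratio.
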